- (1) Lower limb sensation will be measured using a monofilament threshold test (i.e., lower limb sensation test)¹⁴ on the most affected limb at baseline. The scores will be recorded in the **Lower Limb Sensation Test Scoring Sheet**.
- (2) Activity will be measured using the number of steps taken and period of time the subject is sedentary with a Fitbit activity tracker and the TENS device's Quell App.
- (3) Ankle range of motion will be measured using a tape measure while the subject performs the weight-bearing lunge. The resulting measurements will be recorded in the **Ankle Range of Motion** form. This method has been shown to have good reliability when administered by a novice rater.¹⁵

Patient reported outcome measure (PRO):

(1) Fatigue will be assessed using the **PROMIS Fatigue** – Short Form. The PROMIS Fatigue – Short Form was created using a multisite project developed by a clinically relevant and psychometrically quality of life assessment tool for adults and children with neurologic disorders. The measure uses a verbal rating scale (VRS) with anchors "never", "rarely", "sometimes" "often ", or "almost always" [1 = never, 5 = almost always].

Page 5 of 26

Mood, Stigma, and Sleep will be assessed using modified version of Chronic Venous Disease Quality-of-Life Questionnaire (CIVIQ 20), which was developed based on a clinically relevant and psychometrically quality of life assessment tool for adults. The validity was assessed using Cronbach's alpha coefficients and multi-trait/multi-item matrix analyses. The CIVIQ 20 consists of a VRS asking subjects to report whether they have experienced any of specific emotions over the past three weeks using a 1 – 5 Likerttype scale, with anchors "not at all", "a little", "moderately", "a lot", or "completely" [1 = not at all, 5 = completely].

Single-Item Questions:

- (1) **Expectation Questionnaire**. The subject's expectation of device efficacy will be assessed by asking the subjects: "How much do you expect the TENS device will improve your edema symptoms?" using a 1-5 Likert-type scale, with anchors "not at all", "a little bit", "quite a bit", "very much", or "completely" [1 = not at all, 5 = completely].

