To ensure appropriate safety precautions related to COVID-19 when conducting in-person study procedures, the process for conducting in-person visits outlined in the Guidance for Human Subjects Research will be followed.

(https://www.urmc.rochester.edu/coronavirus/coronavirus-research/guidanceforresearchers/human-subjects-research.aspx). A RSRB approved flyer is available to help subjects understand what they can expect when a study visit occurs.

Table 2: Schedule of events

| Events | Pre- Baseline visit (Visit 1) | Baseline period (1 week) | Baseline visit (Visit 2) | Treatment period (3 weeks) | Treatment endpoint (Visit 3) |
|--|--|--------------------------------|--------------------------------|----------------------------|------------------------------------|
| Final eligibility check* | X | | | | |
| Consent | X | | | | |
| Instruct subjects how to use Fitbit device | X | | | | |

Page 11 of 26

| Instruct subjects how to complete at-home paper PROs | X | | | | |
|---|---|---|------------|---|---|
| Use Fitbit daily | | X | | X | |
| Complete daily or weekly at-home paper PROs | X | X | | X | |
| Distribute of study TENS device and teach subject how to use it | | | X | | |
| Complete visit electronic PROs | | | X | | X |
| Functional exam measures | | | X | | X |
| Leg measurements | X | | X | | X |
| COVID Screening form | X | | X | | X |
| Open subject's Quell App and Fitbit while connected to Wi-Fi | | | X 1 | | X |
| Adverse event monitoring ² | | | | X | X |
| Qualitative interview | | | | | X |

^{*}If edema has not been assessed by a clinician within 6 weeks of Pre-baseline visit.

SCREENING / CONSENT

Reminder 1: (phone call) (1-2 days prior to Visit 1). Remind the potential subject (and record in the **Telephone Contact Form**):

- To complete the COVID-19 pre-screen questionnaire prior to the visit.
- Of the date, time of their Visit 1.

Visit 1: Pre-baseline (In-person / Day -7)

If the potential subject has not had the severity of their edema evaluated by the clinician within 6 weeks of the Pre-baseline visit, the severity of their pitting of edema will be evaluated at the Pre-baseline visit by the trained study staff to confirm final eligibility prior to obtaining informed consent.

The coordinator will perform the informed consent process as per description above. The coordinator will confirm whether the subject has received a copy of the URMC and Affiliates

Page 12 of 26

¹ Pair only the Fitbit device

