² Additional phone call after 1 week of TENS use

Notice of Privacy Practices; if not, the subject will receive a copy of the URMC and Affiliates Notice of Privacy Practices.

The coordinator will confirm the following with the subject: whether the subject has active email for preferred method of contact, active Phone # for preferred method of contact, whether or not it is acceptable to leave messages about the study at the provided phone number

The coordinator will perform leg measurements and document them. The coordinator will help the subject setup the Fitbit device, review the user guide and discuss how to use the Fitbit. They will ask the subjects to use the Fitbit at all times (unless they cannot tolerate it while sleeping) until Visit 2.

The coordinator will help the subject register or create an account for direct payments through Advarra Participant Payments, if they do not already have one. The coordinator will provide the subject with the Information Sheet for Advarra Participant Payments. The coordinator will review the two visits that study payments will be initiated through the direct payment system.

The subject will report any medications that could affect their edema. In addition, a coordinator will check the medical record for medications that may cause swelling. The subject will be asked to write in these medications on the medication diary in which the subjects will be asked to document use of medications that could affect edema.

The coordinator will explain how to complete the at-home (paper) PROs.

PRE-BASELINE ASSESSMENT PERIOD

Week -1: (subject will complete at home)

- Subject will use the Fitbit device at all times while awake.
- Subject will setup their Advarra account and choose payment type payments
- Subject will complete the Edema Symptom Pre-Baseline Daily Diary.
- The coordinator will setup times and dates for the **Baseline visit**, **Treatment period Endpoint** visit and follow-up phone call.

.

Reminder 2: (phone call or email) (1 day prior to Visit 1)

Remind the subject (and record in the **Telephone Contact** form):

- Of the date, time, and location of their next in-person study visit.
- To complete the COVID-19 pre-screen questionnaire prior to the visit.
- To complete the visit PROs online via REDCap prior to the visit.
- To bring their completed at-home (paper) PROs from Week -1.
- To bring their Fitbit and mobile device.
- To wear pants with a loose leg.

Page 13 of 26

TREATMENT PERIOD

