Visit 2- Baseline visit: (In-person / Day 0 up to + 5_days)

The coordinator will download the Quell App to the subject's mobile device, setup a Quell Health account for the subject (using valid de-identified study email address and password) and help them pair the TENS device to their mobile device and calibrate it. They will introduce the concept of TENS and describe how it is likely to feel to the subjects using a standardized script. They will give the subject 2 electrode strips along with the TENS device, which should be sufficient for the 3-week duration of the treatment period of the study. They will provide the subject with the subject guide to help them with at-home use and ask them to use the device between 7 to 8 hours per day. They will also ask them to open the Quell App once a day while the device is connected to cellular data or Wi-Fi to transfer the data to the Quell Health account. If the subject plans to use cellular data, the coordinator will setup the Quell App to allow the use of cellular data in the settings.

The coordinator will review the Edema Symptom Daily Diary, Edema Symptom Inventory Week Recall, and Edema Symptom Inventory-Week Recall 0-10 Scale forms and teach the subject how to complete them.

The coordinator will perform the ankle range of motion and lower limb sensation tests and measure the subject's lower limbs using the volumeter and tape measure.

The subject will complete the visit related patient-reported outcome measures (PROs) at the study visit if they were not completed previously using the REDCap link.

Weeks 1-3: (subject will do at home)

- Subject will use the Fitbit Device at all times.
- Subject will use the TENS device for 7 to 8 hours / day either day, night, or asleep.
- Subject will complete the Edema Symptom Daily Diary, Edema Symptom Inventory Week Recall, and Edema Symptom Inventory-Week Recall 0-10 Scale.

Phone Call 1: (Day 7, up to +2 days)

- AE assessment: The coordinator will ask the subject using an open-ended question whether any new symptoms have occurred since starting the study. If so, the coordinator will record the AE in the **AE form** in REDCap.
- Adherence discussion: The coordinator will discuss any adherence problems observed in the data from the Quell App.
- Reminder 3: remind the subject (and record in the **Telephone Contact Form**):
- To complete at-home (paper) PROs for Week 2 (Days 7-14).

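### The baseline-week Fitbit wear instruction contradicts itself and matches the treatment-period instruction in neither version, so the change in sedentary time may partly reflect wear time

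*Combined protocol and SAP*

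**What the plan says.** All references are to the combined protocol and SAP.

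- **Outcome.** Section 4 (exploratory objective assessments) defines activity as "the number of steps taken and period of time the subject is sedentary with a Fitbit activity tracker and the TENS device's Quell App".
- **Baseline week, Visit 1 (section 8).** "They will ask the subjects to use the Fitbit at all times (unless they cannot tolerate it while sleeping) until Visit 2".
- **Baseline week, Week -1 at-home list (section 8).** "Subject will use the Fitbit device at all times while awake".
- **Treatment, Weeks 1-3 at-home list (section 8).** "Subject will use the Fitbit Device at all times".
- **Table 2.** The row "Use Fitbit daily" is marked for the baseline period and the treatment period. It gives no hours and does not mention sleep.
- **Quell App.** Set-up is first described at Visit 2: "The coordinator will download the Quell App to the subject's mobile device". The Table 2 footnote for that visit reads "Pair only the Fitbit device".
- **Analysis (section 16).** Continuous exploratory outcomes are compared between Baseline and Treatment Period Endpoint, using methods similar to the Wilcoxon signed-rank test planned for the primary efficacy outcomes. A separate item inspects Fitbit activity trajectories against swelling ratings by eye. Missing data receive no statistical handling.

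**The concern.** A change score for sedentary time is interpretable only if the tracker is worn over comparable hours in both periods, or if the analysis corrects for hours worn. The plan secures neither. A subject who follows the Week -1 list takes the tracker off at night. The same subject, following the Weeks 1-3 list, keeps it on. Overnight hours are still hours, so if they are counted as sedentary the treatment period gains sedentary time with no change in behaviour.

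Three features of the plan would let such an artefact through:

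- With a single arm, no control group shares the artefact and cancels it.
- No text defines sedentary time, minimum wear, a waking window or the treatment of sleep.
- The Day 7 and Day 14 reminders prompt consistent Fitbit use. The reminder before the Baseline visit asks only that the device be brought along, so prompting to wear it is concentrated in treatment.

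At stake is one of the two measures of an exploratory outcome. Activity by tracker is named in Specific Aim 2, and its results could inform the design of the follow-on trial.

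**Working it through.** The plan states no figure for activity or sedentary time, and the sample of 52 is justified by feasibility, so there is nothing to reproduce. The check is a comparison of texts, followed by an illustration of size.

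**Step 1. The instructions side by side**

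| Place in section 8 | Period | Night wear |
|---|---|---|
| Visit 1 | Baseline week | Requested, with an exception for intolerance during sleep |
| Week -1 list | Baseline week | Not requested |
| Weeks 1-3 list | Treatment | Requested, no exception |
| Table 2 | Both | Silent |

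The two baseline-week entries disagree with each other. Neither is identical to the treatment entry: the Visit 1 version differs by its sleep exception, the Week -1 version by leaving out the night altogether. Table 2 does not settle the matter.

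**Step 2. What must hold for the change score to be distorted**

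1. Some subjects wear the tracker overnight in treatment but not in the baseline week.
2. Overnight hours are counted as sedentary time.
3. The analysis does not adjust for hours worn.

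The documents permit all three. They establish neither the first nor the second. On the third, no adjustment is stated.

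**Step 3. Quell App**

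The app and the TENS device reach the subject at Visit 2, after the baseline week. A Quell value for that week therefore cannot exist, and a Quell change from baseline cannot be computed. A comparison of Fitbit with Fitbit is unaffected.

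**Step 4. Illustration of size (assumed inputs, not from the documents)**

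Let f be the share of subjects who add night wear only in treatment, and h the hours per night then counted as sedentary. The shift in mean daily sedentary time is f × h × 60 minutes.

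- f = 0: 0 min/day.
- f = 0.10, h = 6 to 8: 0.10 × 6 × 60 = 36 to 0.10 × 8 × 60 = 48 min/day.
- f = 0.25, h = 6 to 8: 0.25 × 6 × 60 = 90 to 0.25 × 8 × 60 = 120 min/day.

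A simulation of the signed-rank test used 52 subjects with complete data, no true change, an assumed SD of change of 60 or 120 min/day, a two-sided 0.05 level and 1,000 runs per setting. Rejection was about 4-5% at f = 0, about 20-22% at f = 0.10 and about 80% at f = 0.25. If sleep is excluded, h is 0 and the shift is 0 for every f.

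**The case against.** A reader might infer that baseline wear is confined to waking hours, that treatment wear is round the clock, and that the comparison therefore certainly uses unlike data. The documents do not support that. The instruction the coordinator gives in person at Visit 1 asks for night wear in the baseline week, with an exception only for those who cannot tolerate it. A subject who cannot tolerate it then may well not tolerate it later, so wear within a subject could match. How the tracker records sleep is not stated either. This part of the objection stands: the contradiction in the text is firm, and the bias is a risk.

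A reader might also infer that the missing Quell baseline spoils the activity comparison. It does not. At Visit 3 the Fitbit is paired to transfer activity data while the TENS device is paired for adherence data, and the trajectory item in section 16 names the Fitbit alone. Nothing says the two sources will be pooled. What remains is that section 4 lists Quell as an activity source and section 16 does not say which source supplies the change score.

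Three further limits are fair. Inflated sedentary time would count against TENS and would not create a false benefit. Nothing shows that night wear would distort step counts. The trajectory item is a visual inspection that does not name sedentary time, and the wear instruction is constant across Weeks 1-3.

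The objection does not remove the defect. The Visit 1 exception runs only to Visit 2 and the Weeks 1-3 list has none, so even the more favourable baseline version is not the treatment instruction.

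**Conclusion.** The point holds as a contradiction in the baseline-week instruction, a mismatch of both versions with the treatment instruction, and the absence of any wear or sleep rule for an outcome that depends on wear. The change in sedentary time may consequently reflect wear as well as activity.

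No size can be derived from the documents. The figures in the working show only that a modest share of subjects changing their night wear would matter if sleep counts as sedentary. They rest on assumed shares, hours and SDs, and they fall to zero if subjects follow the Visit 1 request consistently in both periods or if sleep is excluded. They should not be quoted as an estimate of bias in this trial.

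The consequence is confined to an exploratory outcome. Screen failure, refusal and outcome completion do not depend on tracker wear hours as an activity measure, and the water displacement and diary analyses do not use the tracker.

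**What to change.** 1. In section 8, give one identical Fitbit wear instruction at Visit 1, in the Week -1 list and in the Weeks 1-3 list, including the same treatment of sleep.
2. In section 16, add wording such as: *Change in steps and sedentary time is computed from Fitbit data recorded during waking wear only, on the same basis in the baseline week and the endpoint week (for example, per hour worn). Quell App activity is summarised descriptively for the treatment period only.*
3. Say beside it how waking wear will be identified and which days form the endpoint week, since the rule cannot be applied without both.

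The cost is wording in three places plus a short analysis statement. The downside is small: overnight data are not used in the activity change score. If data have already been collected, the analysis statement still helps, provided hours worn can be recovered from the tracker records. Label: cheap improvement.

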Page 15 of 26

Table 3: Edema schedule of data collection.

| FORMS | Screening | Prebaseline period | Treatment period | Treatment period Endpoint |
|---|-----------|-----------------------|------------------|---------------------------------|
| Subject Forms (REDCap or paper) | | | | |
| On Study | | X | | |
| Edema Symptom Daily Diary | | | X | X |
| Edema Symptom Daily Diary-Pre-baseline ¹ | | X | | |
| Impression of Change in Edema Symptoms | | | | X |
| Expectation Questionnaire ³ | | | X | |
| CIVIQ 20 ³ | | | X | X |
| LYMQOL ³ | | | X | X |
| PROMIS Fatigue ³ | | | X | X |
| Edema Interference Questionnaire ³ | | | X | X |
| General Impression of Edema ³ | | | | X |
| General Impression of Activity ³ | | | | X |
| Edema Symptom Inventory-Week Recall | | X | X | X |
| Edema Symptom Inventory-Week Recall 0-10 Scale | | X | X | X |
| Treatment period Endpoint-Qualitative Feedback | | | | X |
| Coordinator Forms (REDCap or paper) | | | | |
| Eligibility checklist (Medical record, Clinicianreported, and Patient-reported items) ¹ | X | | | |

Page 16 of 26 Version Date: 12/8/2020

| Consent form | X | | |
|--------------------------------------|---|---|---|
| Clinical Record Information | X | | |
| TENS Device Settings | | X | |
| Coordinator Lower Limb Swelling | X | X | X |
| Volumeter Measurements | | X | X |
| Lower Limb Sensation Threshold | | X | X |
| Ankle Range of Motion | | X | X |
| COVID pre-screen form | X | X | X |
| Telephone Contact | X | X | X |
| Adverse Event (AE) form ² | | | X |

¹ Forms are completed during the weeks 1, 2, and 3 and being returned by mail to the research team.

General policies regarding contacting subjects: If subjects have chosen to be contacted by email but do not respond to email reminders, they will be called up to 2 times for that specific reminder. If a subject does not attend a phone Call or in-person visit, they will be called up to 3 times to try and reengage the subject in the study. If any phone calls are interrupted or stopped short for any reason, including technological difficulties, a subsequent phone call will be setup to complete the necessary research tasks. Rescheduling of visits can occur up to 1 week after the original visit was scheduled, which will be scheduled within the time-frame indicated in the protocol section for each visit.

The only difference between the commercially-available TENS device's programming and the study TENS device is the size of the intensity increase with a button tap. The maximum allowable intensity is the same as the commercially-available TENS device. Thus, there is no major safety concern if a subject fails to return to the study and continues to use one the study devices, therefore no further attempts other than those outlined above will be made to contact subjects to retrieve the study TENS devices to minimize intrusion in subjects' lives.

Page 17 of 26

² Adverse events will also be assessed after Week 1 via phone

³ Form can be completed via REDCap by subject prior to or at Visit 1, Visit 2, and Visit 3

9. RISKS TO SUBJECTS

Potential risks from stopping use of compression stockings or wraps: If subjects choose to forgo use of compression stockings or wraps to start the trial, there is a risk that their edema could worsen during the study. We have minimized this risk by only enrolling subjects who are not experiencing a significant of benefit from these therapies (i.e., entry criteria: "based on shared decision making of the potential subjects' clinician or the clinician co-investigator [the potential subject is] receiving sufficiently little benefit from these therapies to warrant stopping their use for the duration of the study"). Subjects will be asked to call the study staff if they feel as though their swelling or symptoms are worsening and they will decide together with the clinician Co-I if they should stop using the TENS device and resume using compression stockings or wraps.

Potential risk of not trying currently available treatment options: For some people, the following treatments can be tried for peripheral edema, (1) compression stockings, (2) Velcro wraps, (3) manual lymphatic drainage, (4) short stretch bandage wrapping, (5) pneumatic pumps, (6) kinesiotape, (7) acupuncture, and (8) cupping. For potential subjects who have not been offered these treatments in the past, choosing to join the study and forgoing these treatments could lead to a worse outcome than if they tried one of these alternative treatments. The potential subjects will be informed of these alternative treatment options and given the opportunity to consult their primary care physician or the clinician Co-I regarding whether they should consider the alternative treatments prior to starting the study.

Potential risks of the TENS device: The known potential risks include skin irritation at the electrode sites; however, precautions can be taken to minimize the occurrence of skin irritation (i.e., not wearing the device 24 hours/day for multiple days without taking a break). We have also observed new abnormal sensations in the feet with use of the TENS device in a previous pilot study. In all cases we observed these abnormal sensations were reversible upon stopping use of the device. Subjects will be instructed to contact the study team if they experience new, abnormal sensations in their lower limbs. They will discuss these symptoms with the clinician Co-I and decide together whether it is in their best interest to discontinue use of the device. The principal investigator in consultation with the co-investigator have the ability to remove any subject from the study, who in the clinician Co-I's opinion is being exposed to undue risk from adverse events.

Subjects will be instructed that the TENS device should not be used when getting wet (e.g., in the shower or while swimming) or while driving. Having to remove the device (when getting wet) / turn off the stimulation or remove the device (when driving) may cause inconvenience; this potential inconvenience is unavoidable.

Potential risks associated with the Fitbit: Use of the Fitbit requires registering the Fitbit. We will register the Fitbit with a valid de-identified study email address and password. Fitbit Inc. will have access to the subject's Fitbit de-identified data via the secure cloud database up to 90 days after the Fitbit is deactivated and deregistered. This fact is unavoidable and will be clear in the informed consent form.

Page 18 of 26

Risk associated with breach of confidentiality: Although we will do everything in our power to secure the data from the study, there is a risk that someone outside the study staff will gain access to the data. The risk of breach of confidentiality will be minimized by locking paper forms in a secure filling cabinet and storing electronically entered data on a password protected network drive. Data will be entered electronically via the University of Rochester's secure REDCap system or directly into Excel on a University of Rochester computer. Each subject will receive a unique ID number. All data forms will have only the ID number. A master key that links the study ID numbers with the subjects will be kept in a separate file, also on a University of Rochester secured network drive. Only the study staff will have access to the data. The exception is de-identified data that are collected via the Apps, to which the companies (i.e., Neurometrix and Fitbit) will also have access (see subsequent paragraphs).

We will use the Quell App with the TENS device to retrieve the subjects' adherence data while on the study. The Quell App stores the data received from the TENS device. The TENS device transmits data (data received from TENS device) to a secure online cloud database. To protect against data breaches during data transmission from the TENS device to the Quell App the data is encrypted based on an encryption key that is specific to each wearable device. The data from the secure online cloud database will be sent from Neurometrix via encrypted email to the study team. Data from the emails will be downloaded only to URMC encrypted laptops or desktops and stored on password protected URMC network drives.

We will use the Fitbit software with the Fitbit device to retrieve activity data during the study. Data recorded on the subjects' Fitbit device is transferred from the device to cloud servers to URMC laptop secure server. During the transfer of data from the device to the cloud the data is encrypted to protect from data breaches.

The alternative to participation is not participating and continuing usual care with the subject's clinician.

The risks of e-mail use can include but are not limited to the possible introduction of viruses into the subjects' computer systems, the interception, alteration, forwarding, or used without authorization or detection, circulated, forwarded, stored electronically and on paper, the broadcasting of e-mails to unintended recipients due to the nature of e-mail address to be easily misaddressed. To mitigate these risks the following steps and procedures will be taken during the study. Communications between the study team and the subject will be filed stored on a password protected UR drive and discarded once the study is complete. E-mails containing sensitive medical information will be encrypted. Subjects' email contact information will be verified at minimum 3 times during the study.

Advarra will be used as the direct payment system for study payments. During registration or account creation on the site, Advarra may collect any or all of the following subject information, (i) name, (ii) home or business address, (iii) professional information, including specialty or nature of concern, (iv) organization with whom they are affiliated and its address, and (v) email address. When they visit the site using their personal smart device, the site may automatically record information that their browser sends like, the name of the domain and

Page 19 of 26

host from which they access the Internet; the Internet Protocol (IP) address of the computer or smart device they are using; the date and time they access the site or make uploads or post to the site; and the Internet address of the website from which they linked directly to the site. This information does not include any Personally Identifiable Information and we refer to this information as non-identifiable information.

There is still a risk that a third party could gain access to any Information provided to or collected through this site. To mitigate these risks, any data breaches and, potential identification of the subjects, Advarra has security measures in place to protect electronically transmitted information. They are frequently reviewing and consistently trying to improve the security of the site. They do not collect and subjects will not be asked to submit any "protected health information" as defined in HIPAA.

